5.3.2.2 Ancillary Clinical Proof-of-Principle Part

Subjects are not eligible for the ancillary cPoP part of the trial if they fulfill any of the following exclusion criteria:

1. History of difficulty swallowing, malabsorption or other chronic gastrointestinal disease or conditions that may hamper compliance and/or absorption of the IMP
2. History of any other significant medical disease such as major gastric or small bowel surgery, recent drainage of significant volumes of ascites or pleural effusion (as per Investigator's judgement) or a psychiatric condition that might impair the subject's well-being or preclude full participation in the trial
3. Known hypersensitivity to the trial treatment or to one or more of the excipients used
4. Pregnancy or lactation period
5. Legal incapacity or limited legal capacity
6. Subjects currently receiving (or unable to stop using prior to receiving the first dose of trial drug) medications or herbal supplements known to be potent inhibitors of CYP3A or CYP2C19 must stop at least 1 week prior to taking M3814. Subjects receiving potent inducers of CYP3A or CYP2C19 must stop at least 3 weeks prior to taking M3814. Those receiving drugs mainly metabolized by CYP3A with a narrow therapeutic index as judged by the Investigator (and after optional consultation with the Sponsor) must stop at least one day prior to taking M3814.

5.4 Criteria for Initiation of Trial Treatment

This is an open label trial without randomization. Subjects who provide written informed consent and who meet all relevant eligible criteria will receive open label M3814 at the currently recruiting cohort dose level.

5.5 Criteria for Subject Withdrawal

5.5.1 Withdrawal from Trial Therapy

The subject must be withdrawn from IMP in the event of any of the following:

- Occurrence of an exclusion criterion which is clinically relevant and affects the subject's safety, if discontinuation is considered necessary by the Investigator and/or Sponsor prior to treatment completion
- Therapeutic failure requiring urgent additional drug (if applicable)
- Discontinuation of RT
- Adverse drug reactions (ADRs) that cause RT delays of >7 days

- Occurrence of AEs, if discontinuation of trial drug is desired or considered necessary by the Investigator and/or the subject (if applicable)
- Occurrence of pregnancy
- Use of a nonpermitted concomitant drug, as defined in Section 6.6, where the predefined consequence is withdrawal from the IMP
- New standard existing therapy that is considered more suitable according to the Principal Investigator
- Noncompliance that is deemed by the Investigator or the Sponsor to compromise subject safety or trial integrity.

5.5.2 Withdrawal from the Trial

Subjects are free to discontinue the trial at any time without giving their reasons.

A subject must be withdrawn in the event of any of the following:

- Withdrawal of the subject's consent
- Participation in any other trial during the duration of this trial (up to 12 months in Phase Ia and Ib parts and up to 32 days in the ancillary cPoP part)
- Pregnancy prior to treatment completion or up to 30 days after RT.

If a subject has failed to attend scheduled trial assessments, the Investigator must determine the reasons and the circumstances as completely and accurately as possible.

In case of premature withdrawal from the trial, assessments for Fraction Day 10 (Arm A) or last Fraction Day (33 to 35; Arm B) in Phase Ia, Fraction Day 33 (NSCLC cohort) or last Fraction Day (33 to 35; SCCHN cohort) in Phase Ib and the EOT visit should be performed, if possible with focus on the most relevant assessments ([Table 1](#) [Phase Ia – Arm A capsule cohorts], [Table 2](#) [Phase Ia – Arm A tablet cohorts], [Table 3](#) [first 3 subjects in Phase Ib – Arm A, NSCLC cohort], [Table 4](#) [Phase Ib – Arm A, NSCLC cohort], [Table 5](#) [Phase Ia: – Arm B, SCCHN cohort], [Table 6](#) [Phase Ib – Arm B, SCCHN cohort], and [Table 7](#) [ancillary cPoP part of the trial]). In any case, the appropriate electronic Case Report Form (eCRF) section must be completed.

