Trial Periods	Screening	DLT Evaluation Period						DLT Period/Short-term Safety FU	Mid-term Safety FU	Long-term Safety FU/ EOT ^a	Survival FU
		Treatment Period (M3814 + RT)									
Trial Days	Day -21 to Day -1	FD 1 to FD 33						PTD 1 to 37	PTD 1 to 90	PTD 31 to 365	-
M3814 RT 2 Gy x 33 (5 F/W) ^b		X X									
Visit Days	-21 to -1	FD 1	FD 2	FD 6	FD 10 ^c	FD 16, 21, 26 and 33/ETT ^d	PTD 8, 15, 22, 37 ^e	PTD 84	PTD 42, 126, 168, 180, 210 ^x , 270, 312 ^x , and 365	-	-
Visit Window (days)	-	-	-	-	-	-	±2	±7	±7	-	-
Archival tumor material ^u	X										
CCI											
Survival											X ^y

AE = adverse event; CT = computed tomography; CCI [REDACTED]; DLT= dose limiting toxicity; ECG = electrocardiogram; ECOG PS = Eastern Cooperative Oncology Group performance status; EOT = End of Trial; ETT = Early Treatment Termination; FD = fraction day; FU = follow-up; F/W = fraction per week; Gy = Gray; HCG = human chorionic gonadotropin; HIV = human immunodeficiency virus; MRI = magnetic resonance imaging; CCI [REDACTED]; CCI [REDACTED]; PK = pharmacokinetics; PTD = Post-treatment Day; QTcF = Fridericia-corrected QT interval; RECIST = Response Evaluation Criteria in Solid Tumors; RT = radiotherapy; SMC = Safety Monitoring Committee.

Note: Fraction Day (FD): days when RT and M3814 is given. Post-treatment Day (PTD): days in the period starting as of end of the treatment period until 1 year later.

- All subjects will be followed up for survival until 12 months after the last subject has stopped RT/CRT. All subjects will be followed up for response until 12 months after RT is completed, or earlier due to any reason whereby tumor assessments are no longer applicable (e.g., if a new treatment is started, withdrawal of consent). The reason for early discontinuation should be captured in the source document. If EOT occurs before PTD 365, all assessments must be done as planned for PTD 365. After completing the PTD 365 visit, subjects will be followed up for survival via phone call every 3 months, wherever possible.

- b. RT to be given 1.5 hours (\pm 30 minutes) after dosing.
- c. If FD10 is on a Friday, PK, PD, safety laboratory, and urinalysis sampling must be done on FD9.
- d. FD 33 is the day of the last dose of RT. In case of premature withdrawal during the treatment period, the investigations scheduled for the visit on FD 33 should be performed. In such cases, this visit will be considered the Early Treatment Termination visit.

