- a. All subjects will be followed up for survival until 12 months after the last subject has stopped RT/CRT. All subjects will be followed up for response until 12 months after RT is completed, or earlier due to any reason whereby tumor assessments are no longer applicable (e.g., if a new treatment is started, withdrawal of consent). The reason for early discontinuation should be captured in the source document. If EOT occurs before PTD 365, all assessments must be done as planned for PTD 365. After completing the PTD 365 visit, subjects will be followed up for survival via phone call every 3 months, wherever possible.
- b. RT to be given 1.5 hours (\pm 30 minutes) after dosing.
- c. If FD10 is on a Friday, PK, PD, and safety laboratory sampling must be done on FD9.
- d. FD 33 is the day of the last dose of RT. In case of premature withdrawal during the treatment period, the investigations scheduled for the visit on FD 33 should be performed. In such cases, this visit will be considered the Early Treatment Termination visit.
- e. Hepatitis B and C testing to be performed at Screening unless obtained within 3 months prior to Screening. Screening for HIV will be performed according to local practice and local regulatory guidance.
- f. Heart rate, diastolic and systolic blood pressure, body temperature, and body weight. See Section [7.4.4](#) for details.
- g. Height measured at Screening only.
- h. Physical exam will report findings in the irradiated area during all FU periods.
- i. Evaluation of ongoing treatment-emergent adverse events.
- j. See [Table 15](#) for details of hematology tests.
- k. See [Table 15](#) for details of serum chemistry tests.
- l. Urinalysis: dipstick followed by microscopic examination if abnormal results.
- m. 12-lead resting ECG in triplicate.
- n. 12-lead ECG to be performed predose and once at 2 to 3 hours postdose.
- o. 12-lead ECG to be performed at 2 hours postdose.
- p. Tumor imaging by CT or MRI at baseline to document extent of lesions and absence of metastases (M0 stage) according to RECIST v1.1. Baseline tumor evaluation can be up to 28 days old when treatment starts.
- q. Tumor assessments to be done at long-term safety FU (every 6 weeks during Day 31-180 [4 assessments] and every 13 weeks during Day 181-365 [2 assessments]). Tumor assessment will not be repeated on PTD 180.

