Following completion of the screening and baseline evaluations, subjects enrolled in the ancillary cPoP part of the trial will receive a single high dose of RT (10-25 Gy) on Lesion 1 on Day 1 and on Lesion 2 on Day 2. A single dose of the capsule formulation of M3814 will be administered on Day 2, 1.5 hours (\pm 30 minutes) before the start of RT (see Section 6.3.2 for details on dosing). Three fixed dose levels are planned (100 mg, 200 mg, and 400 mg) (see Table 12 for details).

The ancillary cPoP part of the trial will initially be conducted with the capsule; however, additional cohorts of M3814 (CC1 formulation) may be introduced. The starting dose and subsequent dose levels of M3814 (CC1 formulation) will be defined by the SMC based on PK and safety data generated in ongoing clinical studies evaluating the safety, tolerability, PK, and PD of M3814 (CC1 formulation).

It is planned to enroll 11 subjects with (sub)cutaneous tumor/metastases in the ancillary cPoP part of the trial using M3814 capsule formulation and approximately 12 additional subjects with (sub)cutaneous tumor/metastases using M3814 [CC1] formulation.

Follow-up Periods

Phase Ia/Ib

The follow-up period for all subjects in the Phase Ia and Ib parts of the trial will consist of the following:

- DLT Period: A 5-week (Arm A) or 12-week (Arm B) DLT period after the first dose of M3814 for the evaluation of 'acute' systemic and local toxicity in all subjects in Phase Ia and a 12-week DLT period after the first dose of M3814 in the first 3 subjects of the safety run-in part in the NSCLC expansion cohort during Phase Ib (Arm A)
- Short-term Safety Follow-up: A follow-up for a period of 30 days after the end of RT for evaluation of safety
- Mid-term Safety Follow-up: A safety follow-up period of 3 months after end of RT to evaluate signs of RT-induced toxicity on normal surrounding tissues
- Long-term Safety Follow-up: A safety follow-up period until 12 months after end of RT to evaluate late signs of RT-induced toxicity on normal surrounding tissues
- Survival Follow-up: A follow-up period that will continue until 12 months after the last subject has stopped RT/CRT.

Ancillary cPoP part

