(> 100 / < 400) ^c	(3)

cPoP = clinical proof-of-principle; CCI = CCI PK = pharmacokinetics; RP2D = recommended Phase II dose; SMC = Safety Monitoring Committee.

- a. Additional cohorts of M3814 (CCI formulation) may be introduced. The starting dose and subsequent dose levels of M3814 (CCI formulation) will be defined by the SMC based on PK and safety data generated in ongoing clinical studies evaluating the safety, tolerability, PK, and pharmacodynamics of M3814 (CCI formulation).
- b. At the RP2D an additional 2 subjects will be included making 5 subjects at the RP2D.
- c. Additional doses might be opened upon SMC decision.

Dose Interruption and Dose Reduction

Please refer to Section 6.3.1 for detailed information.

All treatment with M3814 will be given in combination with RT; therefore, a delay in RT would lead to a delay in treatment with IMP. See Section 6.6.3.1 for details on handling RT treatment delays.

Definition of Dose Limiting Toxicity

Dose limiting toxicities will be used to determine dose escalation, same dose level extension, and de-escalation and to determine the MTD taking into account the known toxicities with RT alone. DLT is defined in Section 7.4.1.5.

Definition of MTD

The MTD will be defined by the SMC based on the results from all dose escalation cohorts within each arm. See Section 8.1 for details.

Endpoints

Safety will be the primary endpoint for dose escalation in this trial. Other endpoints (PK, PD, efficacy) if available will also be considered. Endpoints are presented in Section 8.3.

Termination of Treatment

Treatment with M3814 will continue until scheduled RT is completed, unacceptable toxicity, withdrawal of consent, or any criterion for withdrawal from IMP occurs (see Section 5.5.1 for criteria). In all cases, when a subject has discontinued all trial treatments for any reason, the Early

Treatment Termination (ETT) visit should be performed. An End of Trial (EOT) visit will be performed on Post-treatment Day (PTD) 365 for those subjects that remain in the trial or in case of premature trial discontinuation prior to PTD Day 365 (see Section 7.1.4).

Withdrawal from the Trial

Subjects will be withdrawn from the trial if they withdraw consent for any further follow-up visits. See Section 5.5.2 for more details.

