6.6.2 Prohibited Medicines

As stated in Section [5.3.2](#), subjects must not have received chemotherapy, immunotherapy, hormonal therapy, biologic therapy, or any other anticancer therapy or any investigational agent

within 28 days of the first dose of IMP administration (6 weeks for nitrosoureas or mitomycin C), except for subjects with rapidly growing tumors localized in the head and neck region or thorax where the treating physician cannot wait for 28 days. These therapies are also prohibited during the treatment period and up to 30 days after RT, with the exception of concurrent cisplatin in the SCCHN population (Arm B). During the treatment period and up to 30 days after RT, any other investigational agent, chemotherapy, extensive RT (involving $\geq 30\%$ of bone marrow) or any other anticancer therapy (biologics or other targeted therapy) and antineoplastic steroid therapy are also prohibited (Phase Ia and Phase Ib only). Use of any investigational agent during the entire trial duration is not permitted.

Medications or herbal supplements known to be potent inhibitors or inducers of CYP3A or CYP2C19, or drugs mainly metabolized by CYP3A with a narrow therapeutic index as judged by the Investigator (and after optional consultation with the Sponsor) are prohibited (see Section 6.6.4 for details).

The solubility of M3814 is pH dependent; therefore, antacid drugs, H₂-blocker and PPIs might affect absorption. H₂-blockers or PPIs should be stopped 5 days prior to the first treatment, and avoided during the entire treatment period with IMP. Antacid drugs should not be taken 1 hour before IMP administration until 2 hours after IMP administration.

If the administration of a nonpermitted concomitant drug becomes necessary during the treatment period, e.g., due to AEs, the subject should be discontinued from the trial treatment and complete all assessments listed under the ETT visit.

See also Section 6.6.4 for details of possible drug-drug interactions with and by concomitant medication.

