7.1.3.5 Long-term Safety Follow-up: Phase Ia and Phase Ib

The following assessments will be performed for all subjects, excluding subjects in the ancillary cPoP part of the trial, on PTD 42, 126, 168, and 180, (Phase Ia and Phase Ib), and on PTD 270 and 365 (Phase Ib only):

- Assessment of vital signs (blood pressure, heart rate, and body temperature), body weight
- Physical examination
- 12-lead ECG including QTcF (Arm B SCCHN cohort only)
- ECOG PS
- Evaluation of all tissues in the RT area
- Evaluation of ongoing TEAEs
- Tumor assessment according to RECIST v1.1, only required if subject has not started a new antitumor treatment. If a new treatment is started, the date (and regimen) must be reported in eCRF.

The following assessments will be performed on PTD 210 and 312:

- Evaluation of long term RT toxicity (subject called by phone).

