7.1.3.6 Survival Follow-up: Phase Ia and Phase Ib

The following assessments will be performed on PTD 270 and 365 (EOT) for patients in Phase Ia, Arm A:

- Assessment of vital signs (blood pressure, heart rate, and body temperature), body weight. Only required for Phase Ia if subject has not started a new antitumor treatment
- Physical examination
- ECOG PS

- Evaluation of all tissues in the RT area
- Evaluation of ongoing TEAEs
- Tumor assessment according to RECIST v1.1. Only required for Phase Ia if subject has not started a new antitumor treatment.

For all patients, the survival follow-up period will continue until 12 months after the last subject has stopped RT/CRT (defined as end of trial; see Section 5.7). After completion of the visit on PTD 365, all subjects will be followed for survival every 3 months via a phone call until the end of the trial.

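### Section 5.5.2 requires withdrawal from the whole trial when a Phase Ia/Ib subject joins another trial and provides no later survival or late-toxicity contact, in conflict with the survival follow-up promised for all subjects

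*Protocol*

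**What the plan says.** Section 5.5.2 of the protocol gives the events on which a subject has to leave the trial. One is "Participation in any other trial during the duration of this trial (up to 12 months in Phase Ia and Ib parts". Section 5.5.1 deals separately with stopping M3814, so the Section 5.5.2 rule concerns the trial as a whole. For a subject who leaves early, Section 5.5.2 asks for the last-fraction-day and end-of-trial (EOT) assessments where possible. It names no later contact.

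Other parts of the protocol describe follow-up without that exception:

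- Footnote a of Tables 3 to 6: "All subjects will be followed up for survival until 12 months after the last subject has stopped RT/CRT".
- Section 7.1.3.6: "For all patients, the survival follow-up period will continue until 12 months after the last subject has stopped RT/CRT".
- Section 5.1, on late toxicity: "Long-term Safety Follow-up: A safety follow-up period until 12 months after end of RT to evaluate late signs of RT-induced toxicity".
- Section 7.1.3.5, on subjects who start another antitumor treatment: "If a new treatment is started, the date (and regimen) must be reported in eCRF". Scans are then no longer required, but the subject stays in follow-up.

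Two further passages touch the rule. Section 5.1.1 says "Subjects will be withdrawn from the trial if they withdraw consent for any further follow-up visits" and refers to Section 5.5.2 for detail. Section 6.6.2 says "Use of any investigational agent during the entire trial duration is not permitted".

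**The concern.** Treatment lasts about 2 weeks (Phase Ia Arm A) to 7 weeks, and the rule runs for up to 12 months, so it acts mainly on follow-up. A subject who receives new therapy in routine care stays under observation. A subject who receives it inside a study must leave. The protocol gives no reason for the difference.

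Entry into another study is commonly prompted by progression, so the subjects removed would tend to be those with a worse outlook. At stake are the Phase Ib overall survival (OS) estimate and the completeness of late-toxicity data. Sections 5.1 and 7.4 plan to collect toxicity for 12 months after radiotherapy, and SAP Section 15.2.3 tabulates late toxicities for Phase Ia.

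**Working it through.** **1. Do the passages agree?**

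| Place | Survival after joining another trial | Late toxicity after joining another trial |
|---|---|---|
| 5.5.2 | Nothing after EOT | Nothing after EOT |
| 7.1.3.6; Tables 3-6, footnote a | Continues for everyone | Not addressed |
| 5.1, 7.1.3.5 | Not addressed | Continues to 12 months; new therapy is no bar |
| 6.6.2 | Not addressed | Not addressed; other investigational agents barred for the whole trial |

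The all-subject statements never mention withdrawn subjects. The footnotes bring the PTD 365 assessments forward if EOT comes early, and then say "After completing the PTD 365 visit, subjects will be followed up for survival via phone call every 3 months, wherever possible". That can be read as survival calls continuing after an early EOT, or as applying only to subjects who reach PTD 365. The text does not settle which.

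**2. Is there an attrition allowance?** The only one is 10% for DLT evaluability in Phase Ia: 78/(1 - 0.10) = 87, and 87 + 54 + 23 = 164, in line with the stated figure of approximately 165. Nothing is allowed for loss of survival follow-up.

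**3. How large could the OS bias be?** The documents give no rates, so every input here is an assumption: median time to progression 6, 9 or 12 months; median survival after progression 6, 9 or 12 months; constant hazards; no death before progression; a share q = 10%, 20% or 30% of progressors join another trial and are censored at progression.

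Let a = ln 2/(median time to progression), b = ln 2/(median post-progression survival), T = 12 months.

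- True survival when joiners and non-joiners share hazard b: S(T) = e^(-aT) + [a/(a - b)] × [e^(-bT) - e^(-aT)]. When a = b this becomes e^(-aT)(1 + aT).
- Kaplan-Meier limit with joiners censored: exp of minus the integral of b·P1/(P0 + P1), where P0 is the progression-free share and P1 the share that has progressed, is alive and has not joined. When a = b this is e^(-aT) × [1 + (1 - q)aT]^(1/(1 - q)).

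Example with both medians 6 months and q = 0.3: aT = 1.386 and e^(-aT) = 0.25.

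- True: 0.25 × 2.386 = 0.597.
- Kaplan-Meier: 0.25 × (1 + 0.7 × 1.386)^(1/0.7) = 0.25 × 2.635 = 0.659.
- Overstatement: 6.2 points.

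Over all nine pairs of medians, the overstatement of 12-month OS in percentage points is:

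| Share joining | Same hazard as other progressors | Joiners' hazard 0.7 times that of others |
|---|---|---|
| 10% | 1.0 to 1.8 | 0.5 to 1.2 |
| 20% | 2.1 to 3.9 | 1.2 to 2.5 |
| 30% | 3.3 to 6.2 | 2.0 to 4.1 |

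The direction is upward in every cell. If survival is still collected after withdrawal, nobody is censored for this reason and the bias is zero.

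For scale, with 27 subjects and a true rate near 68%, the approximate 95% half-width is 1.96 × √(0.68 × 0.32/27) = 0.176, about 18 points.

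**4. Late toxicity.** SAP Section 9 bases proportions on the whole analysis set unless otherwise stated. A Phase Ia subject withdrawn early would therefore stay in the denominator of the late-toxicity table while late events were no longer sought.

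**The case against.** The strongest reply is that the protocol already promises survival follow-up for everyone, so the loss may never occur. That is a fair reading of Section 7.1.3.6 and the footnotes, and it limits the point to a conflict with a possible consequence. It does not remove the conflict, because a site that follows the specific rule in Section 5.5.2 has no instruction to keep calling.

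Four stronger readings are tempting and are not supported:

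- A reader might infer that OS is informatively censored as planned. OS is calculated for the expansion cohorts only (Section 8.5.3.3), neither document gives an OS censoring rule, and SAP Section 4 leaves Phase Ib to a separate plan that is not among the documents reviewed.
- A reader might infer that Section 5.1.1 limits withdrawal to loss of consent. It does not say that no other reason exists, and it points to Section 5.5.2.
- A reader might infer that all late-toxicity information is lost. An EOT visit is requested, SAEs ongoing at EOT are followed to stabilization or outcome (7.4.1.7), and M3814-related SAEs are reportable at any time (7.4.1.3). Scheduled visits and non-serious late events are what is exposed. The effect on the RP2D is also limited: Section 6.6.2 already bars other anticancer therapy and investigational agents until 30 days after radiotherapy, which leaves roughly PTD 30 to 84 before the 3-month review, and subjects who miss the DLT period for non-DLT reasons are replaced.
- A reader might assume that 20-50% of progressors join another trial, which puts the bias at about 2 to 9 points. Nothing in the documents supports that share, least of all for treatment-naïve subjects treated with curative intent.

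It is also fair to say that a second investigational agent makes late toxicity harder to attribute. That is a reason to record entry into the other trial, not to stop observing.

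**Conclusion.** The point holds as an unresolved conflict that should be corrected. Section 5.5.2 requires withdrawal from the trial and provides for no survival or late-toxicity contact after EOT; other sections promise survival follow-up to all subjects.

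The consequence is conditional. If Section 5.5.2 is applied literally and withdrawn subjects are censored at that time, Phase Ib OS would probably be biased upward. Under the assumptions above the overstatement at 12 months is about 0.5 to 6 points. That is smaller than the sampling error of a 27-subject cohort, but unlike sampling error it runs in one direction. OS is a secondary, descriptive endpoint and a 12-month rate is not a named one, so the figure only illustrates scale. The late-toxicity loss is partial. No sample-size figure is affected.

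**What to change.** Amend Section 5.5.2 so that joining another trial does not end data collection:

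- Survival status and the late-toxicity contacts already in the schedule (the PTD 210 and 312 phone calls, and adverse-event outcome to PTD 365) continue unless the subject withdraws consent for follow-up.
- The date of entry into the other trial is recorded, so that later toxicity can be flagged as possibly confounded by the new agent.

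Reconcile Sections 5.1.1, 5.5.2, 6.6.2 and 7.1.3.6 and the schedule footnotes with this. The change concerns data collection only; how the passages bear on trial treatment is for the sponsor to settle. The Phase Ib analysis plan should define OS censoring, report how many subjects are censored because they joined another trial, and include a sensitivity analysis.

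The cost is wording in several sections and a few extra phone calls. The downside is that late toxicity observed after a new agent is harder to attribute.
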